### 2. Sample Size Calculation

The sample size of this study is obtained from the two-way hypothesis testing formula for the two mean values in two independent groups with a confidence index ( $\alpha$ ) of 95% and power of 80%. Results are considered statistically significant if  $p < 0.05$ . The details of the estimated size of the research subject are as follows:

#### Descriptive study: Cross-sectional sampling

$$n = \frac{Z_{\alpha}^2 P(1 - P)}{d^2} = \frac{1.96^2 \cdot 0.4(1 - 0.4)}{0.1^2}$$

$$n = 92,1 \text{ subjects} \rightarrow 93 \text{ subjects}$$

Legends:

N : Number of subjects

$Z_{\alpha}$  : Z value in 95% confidence index = 1.96

P : Long COVID prevalence according to literature = 0.40

d : Standard deviation = 0.10

#### Analytic study: Prospective Cohort, consecutive sampling method

$$n = \left( \frac{Z_{\alpha}\sqrt{2PQ} + Z_{\beta}\sqrt{P1Q1 + P2Q2}}{P1 - P2} \right)^2 = \left( \frac{1.96\sqrt{2 \times 0.553 \times 0.447} + 0.80\sqrt{0.653 \times 0.347 + 0.453 \times 0.547}}{0.20} \right)^2$$

$$n = 93 \text{ subjects} \rightarrow N = 186 \text{ subjects}$$

Legends:

n : Number of subjects

$Z_{\alpha}$  : Z value in 95% confidence index = 1.96

$Z_{\beta}$  : Z value of test power = 0.80

$P_1 - P_2$  : Minimal difference in proportion considered significant = 0.20 ( $P_1 = 0.653$ )

Q : 1 - P

Assuming a 20% loss to follow-up event, the final sample size is:

$$n = 186 + (186 * 20\%)$$

$$n = 186 + 37$$

$$n = \mathbf{223 \text{ subjects}}$$

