Subject Population Key criteria for Inclusion and Exclusion:	
Inclusion Criteria
 
 
1. Adult patients, aged <math>\geq 18</math> years old with a history of laboratory-confirmed SARS-CoV-2 infection via a positive molecular (RT-PCR) or antigen (lateral flow assay) test, receiving outpatient/inpatient care from [name] General Hospital, any time prior to enrollment in this study.
 
2. Patients with/without comorbidities.
 
3. Willing to fill-out online Long COVID symptoms follow-up questionnaire.
 
4. Willing and able to comply with the trial protocol, 6 Minutes Walking Test (re-visits and physical testing).
 
 
Exclusion Criteria
 
 
1. Patients with no registered medical record number (MRN) at [name] General Hospital.
 
2. Refusal to participate in the study or to sign the informed consent form.
 
3. Contraindicated to perform the 6 Minutes Walking Test.
 
4. Patients with no access to a smartphone or computer (desktop, laptop, or tablet) to fill out the online screening questionnaire.
 
5. Patients who died during or before enrollment in the study.
 

Number of Subjects	
A total of 250 subjects are divided into 4 groups according to SARS-CoV-2 vaccination status:
 
 
• Never been vaccinated.
 
• Received 1st dose of vaccination.
 
• Received 2nd dose of vaccination.
 
• Received 3rd dose of vaccination.
 

Study Location	[name] General Hospital, Central Jakarta, Jakarta, Indonesia
Study Duration	Each subject's participation will last for 6 months. The estimated duration for the main protocol is approximately 1 year.
Study Phases	
Screening Screening for eligibility and obtaining consent.
 
Study Examination Online questionnaire filling, 6-Minute Walking Test (6MWT)
 
Follow-up Follow-up examination 3 and 6 months after baseline.

Safety Evaluations	
Adverse events will be monitored and collected by the study team from the point of signed consent until the adverse event(s) are resolved and subjects are stabilized. Adverse events will be managed according to the 6MWT guidelines of the American Thoracic Society (ATS).

---

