### **2. Study Objectives**

#### **2.1. Primary**

- To provide an overview of the symptoms and characteristics of Long COVID patients at [name] General Hospital.
- To determine whether vaccination against SARS-CoV-2 could improve clinical outcomes and quality of life of Long COVID patients at [name] General Hospital.

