## 5.2. Study Population and Selection Criteria

All participants will be required to sign a written informed consent, be willing and able to comply with all study requirements, and should meet the following criteria:

1. Adult patients, aged  $\geq 18$  years old with a history of laboratory-confirmed SARS-CoV-2 infection via a positive molecular (RT-PCR) or antigen (lateral flow assay) test, receiving outpatient/inpatient care from [name] General Hospital, any time prior to enrollment in this study
2. Patients with/without comorbidities
3. Willing to fill-out online Long COVID symptoms follow-up questionnaire
4. Willing and able to comply with trial protocol (re-visits and physical testing)

Subjects will be **excluded** from the study based on the following criteria:

1. Patients with no registered medical record number (MRN) at [name] General Hospital
2. Refusal to participate in the study or to sign the informed consent form
3. Any contraindications for 6 Minute Walking Test according to the guidelines of the American Thoracic Society (ATS)
4. Patients with no access to a smartphone or computer (desktop, laptop, or tablet) to fill out the online screening questionnaire
5. Patients who died during or before enrollment in the study

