## STATISTICAL ANALYSIS PLAN

### 1. Randomization

Subjects who meet all inclusion and exclusion criteria will be allocated into four groups; Never been vaccinated, received 1st dose, received 2nd dose, and received 3rd dose of vaccination. Subject allocation will be carried out through block randomization and known only by the pharmacist, and confidentiality is maintained so that subjects, doctors/nurses, researchers, and data analysers do not know the allocation of each subject.

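### SAP section 2 uses 0.80 as Z-beta and under-allows for loss (223 should be 240); the planned 250 covers this for two near-equal groups, but not for four dose groups or a Long COVID-only analysis

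*Combined protocol and SAP*

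**What the plan says.** SAP section 2 describes the method as a "two-way hypothesis testing formula for the two mean values in two independent groups", with 80% power and a 0.05 significance level. The calculation printed under the analytic study is for two proportions, 0.653 and 0.453. Its legend gives "Z value of test power = 0.80", and 0.80 is the value in the formula. The result is 93 per group and 186 in total. Under the line "Assuming a 20% loss to follow-up event, the final sample size is", 20% of 186 is added to reach 223.

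The synopsis plans more: "A total of 250 subjects are divided into 4 groups according to SARS-CoV-2 vaccination status". Protocol section 5.1 also gives 250. Neither place derives that number. SAP section 1 repeats the grouping: "Subjects who meet all inclusion and exclusion criteria will be allocated into four groups".

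The primary analytic objective (protocol section 2.1) asks whether vaccination "could improve clinical outcomes and quality of life of Long COVID patients". Eligibility (section 5.2) requires only a "history of laboratory-confirmed SARS-CoV-2 infection via a positive molecular (RT-PCR) or antigen (lateral flow assay) test". The descriptive sample size in SAP section 2 takes "Long COVID prevalence according to literature = 0.40".

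**The concern.** There are three errors on the face of SAP section 2: a power is used as a normal quantile, the allowance for loss is multiplied on instead of divided out, and the named method (means) is not the printed one (proportions).

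The larger question is what the 80% refers to. The calculation is for two equal groups with every enrolled subject analysed, apart from the 20% lost. The plan defines four groups by doses received and poses its primary analytic question in Long COVID patients, who are a subset of those enrolled. Vaccination status is recorded by questionnaire (protocol section 5.4) and sampling is consecutive, so group sizes will be whatever the clinic yields. The text does not name the contrast or the population that carries the stated power. A null result from a much weaker comparison could then be read against a claimed 80% and taken as evidence that vaccination does not help.

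**Working it through.** **Inputs from SAP section 2.** Two-sided 0.05 (Z = 1.96); P1 = 0.653; P2 = 0.453; mean P = 0.553; Q = 0.447; difference 0.20; loss 20%. Planned enrolment is 250 (synopsis).

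**Reproducing the plan's figure.**

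n = [(1.96·√(2PQ) + Zβ·√(P1Q1 + P2Q2)) / 0.20]²

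- √(2 × 0.553 × 0.447) = 0.7031, and × 1.96 = 1.3781.
- √(0.653 × 0.347 + 0.453 × 0.547) = 0.6888.
- With Zβ = 0.80: [(1.3781 + 0.5510)/0.20]² = 93.04. The SAP prints 93, hence 186, and 186 × 1.2 = 223.2, printed as 223.

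**Correcting it.**

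- A Z of 0.80 corresponds to Φ(0.80) = 78.8% power.
- With Zβ = 0.8416: [(1.3781 + 0.5797)/0.20]² = 95.8, so 96 per group and 192 in total.
- Loss: 223 × 0.8 = 178 evaluable, which gives 77% power. The right step is 192/0.8 = 240.
- 250 × 0.8 = 200 evaluable. Power for 100 v 100 is Φ[(0.20·√100 − 1.3781)/0.6888] = Φ(0.903) = 81.7%.

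**Power for other comparisons, 0.653 v 0.453.** For unequal groups the same test is used with the weighted mean proportion:

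power = Φ[(0.20 − 1.96·√(P̄Q̄(1/n₁ + 1/n₂))) / √(P1Q1/n₁ + P2Q2/n₂)]

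A range reflects which group has the higher proportion. The documents give no group sizes, so every split below is an assumption.

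| Comparison (200 evaluable) | Power |
|---|---|
| 100 v 100 | 81.7% |
| 80 v 120 | 80% |
| 60 v 140 | 74–75% |
| 40 v 160 | 62–64% |
| 20 v 180 | 39–42% |
| Four equal groups: no dose v any dose (50 v 150) | 69–71% |
| Four equal groups: one pair (50 v 50) | 52% |
| Four equal groups: overall 4×2 chi-square (3 df) | 36–66% |

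The 80% threshold is a smaller-group share of 0.392 to 0.400. The chi-square range runs from only the two extreme groups differing (36%) to two groups high and two low (66%). With no loss, as for a baseline comparison on all 250, the three four-group rows become 79–80%, 62% and 45–77%.

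**Long COVID patients only.** If the SAP's literature value of 40% applied to those enrolled, 200 × 0.4 = 80 would be evaluable. The 30% and 60% columns are an assumed range around it.

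| Comparison | 30% share (60) | 40% share (80) | 60% share (120) |
|---|---|---|---|
| Two equal groups | 34% | 43% | 60% |
| Quarter v three quarters | 26–28% | 33–35% | 47–49% |
| One pair of four equal groups | 19% | 24% | 34% |

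**Difference detectable at 80% power, centred on 0.553.** 50 v 150: 22.4 to 22.6 points (about 23). 50 v 50: 27.5 points (about 28). 40 v 40: 30.7 points (about 31).

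**The case against.** The strongest reply is that the proven errors have no consequence: 250 exceeds the corrected 240, and two equal groups keep 81.7%. That stands for the arithmetic taken alone.

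A second reply is that a two-group analysis may be what is meant. SAP section 2 speaks of two independent groups, and SAP section 3.2.2 mentions a 2×2 table. That is possible, but the 2×2 wording only sets the condition for Fisher's test and names no contrast. Even no dose against any dose falls to about 70% if the four groups are equal.

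Third, the size of the shortfall rests on unstated inputs. The 40% is a literature prevalence used for the descriptive sample size, and the SAP does not say which outcome or population 0.653 and 0.453 describe. If they describe Long COVID frequency in everyone enrolled (a secondary objective, section 2.2), the Long COVID-only figures do not apply to that endpoint. This is fair, and it is why ranges are given.

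Finally, the figure in SAP section 3.2 and the flow diagram in SAP section 4 were not available for this review and might show the grouping. The remark about an unnamed contrast and population is therefore limited to the text. None of this touches the corrected 96, 192 and 240.

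**Conclusion.** The concern holds. SAP section 2 is wrong as written: 93, 186 and 223 should be 96, 192 and 240, and the method should be named as one for two proportions. The planned 250 absorbs this only when two groups of roughly 40/60 or better are compared in all enrolled subjects with no more than 20% lost.

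The stated 80% does not extend to the four dose groups or to a Long COVID-only analysis. For a 20-point difference, the shortfall is modest for no dose against any dose and large for a single pair or within Long COVID patients. Those sizes depend on the assumed splits, the assumed Long COVID share and the SAP's two proportions. The correction to the sample size depends on none of the assumed splits or shares. It should be fixed before analysis, but it is not a reason to enrol more patients.

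**What to change.** Change the SAP text as follows.

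- **Calculation.** Name the formula as one for two proportions, use Zβ = 0.842, and state 96 per group, 192 in total, 192/0.8 = 240, with 250 planned. Say that this power applies to the scores and walking distance in protocol section 5.4 only if they are dichotomised.
- **Condition on the power.** Add: *With 250 enrolled and 200 evaluable, power for a 20-point difference is about 82% for two equal groups and falls below 80% if the smaller group has less than about 40% of subjects.*
- **Main contrast.** Name one contrast and its population. Give the expected group sizes from vaccination counts at enrolment, taken without looking at outcomes, and report the power they give. Do not call it 80% powered for 20 points unless they support that.
- **Other comparisons.** Label the remaining four-group and Long COVID-only comparisons exploratory, with the difference detectable at 80% power: about 23 points for 50 v 150, 28 for 50 v 50 and 31 for 40 v 40, updated to the actual sizes.

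This needs no extra patients, visits or data. It does require the investigators to decide on the main contrast. The stated power will look less favourable for the four-group and Long COVID-only comparisons, and fewer of them can be presented as confirmatory.

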### **3. Analysis methods**

#### **3.1. Data entry**

Before entering data (data entry), the existing data is edited first to facilitate the stages of data entry. The data entry process goes through the coding process in the SPSS Statistics 20.0 program.

#### **3.2. Data analysis**

[figure not shown]
##### **3.2.1. Univariate analysis**

The analysis is intended to obtain descriptive data regarding the incidence of long COVID events and the characteristic profile of long COVID patients.

##### **3.2.2. Bivariate analysis**

This analysis is used to see the relationship between the effect of the COVID-19 vaccine on clinical long COVID and the quality of life of long COVID patients. The level of significance used is 0.05. Variables are statistically significant if p-value <0.05. The independent variables in this study are nominal scale, so the test used in this analysis is the chi-square test or fisher's test (in the group of independent variables with a dichotomous scale of 2x2 if the chi-square does not meet the requirements.

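### The primary vaccine comparison is among Long COVID patients, but the sample size makes no allowance for enrolled subjects without Long COVID, and doses before and after onset are not separated

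*Combined protocol and SAP*

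**What the plan says.** **Who is enrolled.** Protocol 5.2 and the synopsis admit any adult with a past laboratory-confirmed infection treated at the hospital. Long COVID is not an entry criterion. The synopsis and SAP 3.2.1 plan to describe how often Long COVID occurs among participants, so subjects without it are expected.

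**Who is compared.** The primary vaccine objective (Protocol 2.1) asks whether vaccination "could improve clinical outcomes and quality of life of Long COVID patients". The synopsis analysis plan likewise relates vaccination status to outcomes of Long COVID patients. SAP 3.2.2 reads "This analysis is used to see the relationship between the effect of the COVID-19 vaccine on clinical long COVID and the quality of life of" (the sentence ends by naming Long COVID patients), and tests this with chi-square or Fisher's test.

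**How the size was set.** SAP section 2 claims 80% power from a "two-way hypothesis testing formula for the two mean values in two independent groups", although the formula printed is for proportions. The analytic part uses "Minimal difference in proportion considered significant = 0.20" (0.653 versus 0.453) and "Z value of test power = 0.80". It reaches 93 per group, 186 in total and 223 after adding 20% for loss. Planned enrolment is 250. The descriptive part uses "Long COVID prevalence according to literature = 0.40", and that figure does not enter the analytic calculation.

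**Frequency and timing.** Protocol 2.2 makes a reduction in Long COVID frequency a secondary vaccine objective. Protocol 5.4 collects the date of vaccination, but no section relates that date to infection or to Long COVID onset.

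**The concern.** The subjects counted in the sample size and the subjects named in the primary comparison are different sets. If only some of those enrolled have Long COVID, the comparison rests on fewer people than the calculation assumes. A null result could then be read as evidence that vaccination does not help, in a study whose stated purpose is to reinforce vaccine recommendations.

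The second issue is one of interpretation. The plan itself treats Long COVID as something vaccination may prevent. For a dose received before onset, being a Long COVID patient is then partly a consequence of exposure. Vaccinated and unvaccinated Long COVID patients may differ for reasons unrelated to any effect of vaccination on established disease. For a dose received after onset, restricting to Long COVID patients is a legitimate question. The plan pools the two.

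**Working it through.** **Inputs.** From SAP section 2: P1 = 0.653, P2 = 0.453, mean P = 0.553, Zα = 1.96, 20% loss, literature prevalence 0.40. From the synopsis: 250 enrolled. Two equal groups are assumed, as in the plan's formula.

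**1. Reproduce the plan's figure.**
- √(2 × 0.553 × 0.447) = 0.7031
- √(0.653 × 0.347 + 0.453 × 0.547) = 0.6888
- n = [(1.96 × 0.7031 + 0.80 × 0.6888) / 0.20]² = 93.0 per group, so 186 in total
- 186 × 1.20 = 223

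The printed result reproduces. The 0.80 entered for Zβ is the power itself; the normal quantile for 80% is 0.842, which gives 95.8, or 96 per group. True power at 93 per group is 78.8%. That slip is small and separate from this point.

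**2. Power when only Long COVID patients are compared.** Solving the same formula for power with m per group:

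power = Φ[(0.20 × √m − 1.96 × 0.7031) / 0.6888]

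Example at 40% prevalence with 20% loss: 250 × 0.40 × 0.80 = 80, so m = 40. Then (1.2649 − 1.3781) / 0.6888 = −0.164, and Φ(−0.164) = 43.5%.

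| Long COVID prevalence | m, no loss | Power | m, 20% loss | Power |
|---|---|---|---|---|
| 40% | 50 | 52.1% | 40 | 43.5% |
| 60% | 75 | 69.6% | 60 | 59.8% |
| 80% | 100 | 81.7% | 80 | 72.5% |
| 100% | 125 | 89.4% | 100 | 81.7% |

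The no-loss column suits a baseline comparison; the other suits follow-up.

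**3. Prevalence needed to keep 186 evaluable.** With no loss, 186 / 250 = 74%. With 20% loss, 186 / (250 × 0.80) = 93%. At 40% prevalence, enrolment would have to be 186 / 0.40 = 465 with no loss, or 465 / 0.80 = 581.25, so 582, with 20% loss.

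**4. The two readings of the unnamed endpoint.**
- *An outcome in Long COVID patients.* The table applies. At 40% prevalence the stated 80% is not reached.
- *Long COVID occurrence in all enrolled.* The 100% row applies (89.4% / 81.7%), so the calculation is adequate for that question. That question is a secondary objective, and the primary comparison is left without a power calculation.

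**5. Would analysing everyone recover the power?** Suppose the 0.20 difference exists only in the 40% with Long COVID, and that share is the same in both groups. The overall difference becomes 0.40 × 0.20 = 0.08. With 100 per group, power is between 20% and 31%, whatever the outcome rate in the other 60%. The 81.7% for all enrolled holds only if the full 0.20 applies to everyone.

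**The case against.** **The 80% may never have been meant for this comparison.** SAP section 2 names no endpoint, and the phrase "clinical long COVID" in SAP 3.2.2 could mean occurrence among all participants. This stands. A reader might infer that the plan simply fails to deliver its stated power, but the documents do not settle that. They support only the two-way statement in step 4. The quality-of-life part of SAP 3.2.2 and Protocol 2.1 are explicitly about Long COVID patients, so neither reading shows 80% for the primary comparison.

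**The 40% is a literature figure, used for descriptive precision.** This also stands. It is not a forecast for a hospital cohort willing to complete a Long COVID questionnaire, so it would be wrong to present a single power of about 44% as fact. A range is needed. Even so, prevalence would have to be 93% for the planned number to survive the planned loss.

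**Restricting to Long COVID patients fits the rationale.** The introduction speaks of vaccination and the resolution of Long COVID. That is a question about people who have it, and the restriction answers it for doses after onset. This is why the comparison should stay and all enrolled subjects should not replace it as the main analysis set. Such a change would alter the primary question and, by step 5, need not restore power.

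**Four groups make it worse.** One might quote power for a single pair out of four vaccination groups. That is a different problem: 200 evaluable subjects in four groups of 50 give only 52.1% per pair with no Long COVID restriction at all, and the SAP specifies no pairwise tests.

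**Missing figures.** The data-analysis figure and the flow diagram are not shown in the text available, so an analysis set stated there cannot be ruled out.

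**Conclusion.** The concern holds in this form. The primary vaccine comparison is confined to Long COVID patients, enrolment is not, and the analytic sample size allows only for loss to follow-up. The 80% in SAP section 2 is therefore not shown for the primary comparison: it is either not delivered or belongs to a secondary objective. At the plan's 40% prevalence, power is 52.1% with no loss and 43.5% with 20% loss. At 80% prevalence it is 81.7% and 72.5%. These figures assume 0.653 versus 0.453, a two-sided 5% test and two equal groups.

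For doses before Long COVID onset, the restriction selects on an event the plan expects vaccination to change. A reader might go further and infer a bias of known direction, for example against vaccination because vaccinated patients who still develop Long COVID are frailer. The documents do not support that: they give no association between frailty, Long COVID and the outcomes from which a direction or size could be derived. What can be said is that, with the two timings pooled and only unadjusted tests planned, the result cannot be read as an effect on existing Long COVID.

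**What to change.** **SAP section 2.** Name the endpoint and the analysis set for the 0.653 versus 0.453 calculation. For the Long COVID-only comparison, replace the single 80% with power over a range of prevalences, including 43.5% to 52.1% at 40%.

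**SAP 3.2.2.** Keep the comparison among Long COVID patients. Use the vaccination dates collected under Protocol 5.4 to separate doses received before Long COVID onset from doses received after it, and interpret only the latter as an effect on existing Long COVID. Report the same contrasts in all enrolled subjects as a supportive analysis, without claiming that this restores 80% power. The quality-of-life and walking-test data are scheduled under Protocol 5.4 with no restriction to Long COVID, so no new collection is needed for it.

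**Cost.** The stated power becomes less favourable, the groups split by dose timing are smaller, and there is a little more analysis work.

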#### **2.2. Secondary**

- To determine whether vaccination against SARS-CoV-2 could increase functional exercise capacity of Long COVID patients at [name] General Hospital.
- To determine whether vaccination against SARS-CoV-2 could reduce symptoms, duration, and frequency of Long COVID at [name] General Hospital.

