## 5.4. Data Collection

Data on age, sex, height, weight, body mass index, income, education, comorbidities, smoking, alcohol consumption, documented SARS-CoV-2 vaccination

status (including the amount, type, and when the vaccine was received), detailed history of laboratory-confirmed SARS-CoV-2 infection, Long COVID symptoms, severity, and duration are collected through online screening questionnaire.

Data on quality of life (QoL) are collected through St George's Respiratory Questionnaire (SGRQ) and Short Form (SF)-36 Health Survey self-assessment questionnaire at baseline, 3 and 6 months after enrollment. SGRQ addresses QoL in the domains of symptoms, activity, and impacts within the last 4 weeks; and the SF-36 Health Survey questionnaire addresses QoL in the domains of vitality, physical functioning, bodily pain, general health perceptions, physical and emotional and social role functioning.

Data on functional exercise capacity is measured using the Six-Minute Walking Test (6MWT) at baseline, 3 and 6 months after enrollment. The 6MWT is performed according to the guidelines of the American Thoracic Society (ATS). During the 6MWT, such data are collected: Blood pressure, oxygen saturation (SpO2), heart rate, dyspnea, and overall fatigue score using the Modified Borg scale before and after the test, and also one-time measurement (total distance walked in 6 minutes, symptoms at the end of exercise).

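### The exercise-capacity objective has no named analysis, and the only tests offered (chi-square or Fisher) can neither compare metres walked nor adjust for age, sex and height

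*Combined protocol and SAP*

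**What the plan says.** Protocol section 2.2 and the synopsis give as the first secondary objective: "To determine whether vaccination against SARS-CoV-2 could increase functional exercise capacity of Long COVID patients". Section 5.4 states how it is measured: "Data on functional exercise capacity is measured using the Six-Minute Walking Test (6MWT) at baseline, 3 and 6 months after enrollment". The quantity recorded at each test is a "one-time measurement (total distance walked in 6 minutes, symptoms at the end of exercise", so the natural endpoint is continuous, in metres. The same section lists the personal data collected, beginning "Data on age, sex, height, weight, body mass index, income, education, comorbidities, smoking, alcohol consumption, documented SARS-CoV-2 vaccination".

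SAP section 3.2.2, the only between-group analysis in the SAP, concerns "the effect of the COVID-19 vaccine on clinical long COVID and the quality of life of long COVID patients". On method it says: "The independent variables in this study are nominal scale, so the test used in this analysis is the chi-square test or fisher's test". SAP section 3.2.1 is descriptive and covers the incidence of Long COVID and the profile of patients. The synopsis relates vaccination status to patient characteristics and clinical outcomes, again by chi-square or Fisher. Neither SAP section mentions the walk test, a cut-off for distance, change from baseline, a regression model or a covariate.

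**The concern.** A stated objective is measured up to 750 times (250 subjects x 3 visits), yet the text does not say how it will be compared between the dose groups. There are two ways to read the plan. Either exercise capacity is outside section 3.2.2 and the objective goes untested, or it falls under clinical outcomes and is tested by chi-square or Fisher. In the second case distance must first be cut into categories at a point chosen after the data are seen. That loses information and opens a choice that can change the result.

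The reason given for the test does not settle the matter. A nominal explanatory variable does not by itself call for chi-square; the scale of the outcome matters too. A four-level group and an outcome in metres call for a comparison of means.

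Neither test can adjust for covariates. The groups are defined by the vaccination status subjects already have, so differences in age and sex between dose groups are plausible. To the extent that distance depends on age, sex and height, such differences would appear as differences in exercise capacity.

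**Working it through.** **1. The plan's own sample size.** SAP section 2 uses the two-proportion formula with Z_alpha = 1.96, Z_beta = 0.80, P = 0.553, P1 = 0.653 and P2 = 0.453:

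- 1.96 x sqrt(2 x 0.553 x 0.447) = 1.378
- 0.80 x sqrt(0.653 x 0.347 + 0.453 x 0.547) = 0.551
- n = ((1.378 + 0.551) / 0.20)^2 = 93.0, so 93 per group and 186 in total; 186 + 37 = 223.

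The figure reproduces. It sizes a binary outcome in two groups. The documents give no SD, target difference or cut-off for walked distance, so everything below rests on assumed inputs.

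**2. Cost of categorising.** Take the SAP's 93 per group, two groups, two-sided 0.05. A comparison of means has 80% power for a difference of (1.96 + 0.84) x sqrt(2/93) = 0.411 SD. If distance is instead split at the median (an assumption, as no cut-off is given) and the proportions are compared, power for the same difference is about 60%.

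**3. Gain in precision from adjustment.** Assume that age, sex and height explain R2 = 0.2 to 0.4 of the variance in distance at one visit. The SE is multiplied by sqrt(1 - R2):

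| R2 | SE ratio | Fall in SE | Power for 0.411 SD, 93 per group |
|---|---|---|---|
| 0 | 1 | none | 80% |
| 0.2 | 0.894 | 11% | 88% |
| 0.4 | 0.775 | 23% | 95% |

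**4. Possible bias without adjustment.** Assume that two dose groups differ by 5 to 10 years in mean age, that distance falls by 2 to 4 m per year of age, and that the SD is 80 to 100 m. The spurious difference d is then 5 x 2 = 10 m to 10 x 4 = 40 m. With 250 subjects in four equal groups, n is about 62 each (equal split assumed). For a two-sided z-test on means, delta = d / (SD x sqrt(2/n)), and the chance of significance is 1 - Phi(1.96 - delta) + Phi(-1.96 - delta), with sqrt(2/62) = 0.180:

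- d = 10 m, SD = 100 m: delta = 0.557, chance 0.086, about 9%
- d = 40 m, SD = 80 m: delta = 2.784, chance 0.795, about 80%

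With 50 per group (62.5 x 0.8, the plan's 20% loss) the range is 8% to 71%. The nominal rate is 5%. This step prices an unadjusted comparison of means, which the plan does not itself specify.

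**The case against.** Several points on the other side have force.

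- **Coverage.** A reader might infer that the plan contains no analysis of exercise capacity at all. That goes too far. The synopsis term for clinical outcomes is undefined and could include the walk test, although section 2 of the protocol lists clinical outcomes and exercise capacity as separate objectives. A figure under SAP section 3.2 is also not shown. What stands is that no readable text names the endpoint or a test suited to it.
- **Raw means.** A reader might infer that the plan compares raw mean distance and so builds in a known bias. It does not say so; it names only tests for categories. The 9% to 80% range illustrates what an unadjusted comparison of means would risk.
- **Randomization.** SAP section 1 says subjects are allocated to the four groups by block randomization. If true, systematic imbalance would disappear. But the groups are defined by existing vaccination status, and protocol section 5.1 describes a cohort. The two statements must be reconciled. Even under randomization the missing analysis and the gain in precision would remain.
- **Repeated measures.** A change-from-baseline analysis would remove much of any stable effect of age, sex and height on level. This is correct, and it limits step 3 to single-visit comparisons. The plan specifies no such analysis.
- **Assumptions.** The documents promise no standardised distance and give no R2, SD or slope, so adjustment is a recommendation and the size of its benefit is assumed.

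**Conclusion.** The point holds. The first secondary objective has a measurement at three visits but no named comparison, and the only tests in the readable text would need an unstated cut-off and allow no covariates. This follows from the documents and depends on no assumption.

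The size does depend on assumptions: an SE 11% to 23% smaller for a single-visit comparison if R2 is 0.2 to 0.4, and a 9% to 80% chance of a significant result with no vaccine effect if two groups of about 62 differ by 10 to 40 m through age alone. A reader who assumed two groups of 100 would obtain 11% to 94% from the same inputs. The documents do not support that group size, because the plan divides 250 subjects among four groups and does not give the split.

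Nor should adjustment for age, sex and height be taken to make the comparison free of confounding. It removes only those three sources. The plan can be corrected without new data, and the issue affects a secondary objective.

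**What to change.** Add functional exercise capacity to SAP section 3.2.2 as its own analysis:

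- **Endpoint:** distance walked in metres, kept continuous.
- **Model:** a linear model, or a repeated-measures model over the three visits, with dose group as the factor and age, sex and height as covariates. State the visit or contrast that answers the objective.
- **Report:** adjusted mean differences between dose groups in metres, with 95% confidence intervals.
- **Limits:** state that comorbidity, smoking and infection history, all collected, remain as possible confounders unless they are added to the model.

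Reconcile the randomization paragraph in SAP section 1 with the cohort design in protocol section 5.1, and say in the synopsis whether clinical outcomes include the walk test.

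The cost is SAP wording and one extra model. No new variable, visit or subject is needed.
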